1. INTRODUCTION

1.1. Background

What is known

Idiopathic Immunoglobulin A nephropathy (IgAN) is the most common biopsy-proven glomerulonephritis in the world. It is more prevalent in Asia than in Europe and the US (1). IgAN is estimated to affect more than 500.000 people in Europe and it is the leading nephritis in kidney-biopsied patients. Approximately 40% of IgAN patients reach end-stage kidney disease (ESKD) 20 years after their kidney biopsy (2,3). The high prevalence of ESKD shows that IgAN has a significant economic impact in the countries because renal replacement therapy is costly. Moreover, the disease's onset in the second and third decades of life represents a social challenge because patients are typically very active and highly productive in the workplace. This challenge is one more reason to move from a generalized therapy for all patients to personalized therapy.

The first edition of the KDIGO guidelines, published in 2012 (4), suggested different therapeutic approaches for IgAN patients based on the clinical setting. Three sets of patients were considered:

i) *Patients with low risk* manifest minor urinary findings and proteinuria < 0.5 g/day, normal estimated glomerular filtration rate (eGFR) and normal blood pressure; they need only annual or biannual checks without therapy. They represent only 5-10% of the IgAN patient population.

ii) *Patients with intermediate risk* have proteinuria > 0.5 g/day with normal or reduced eGFR and normal or high blood pressure. They may benefit from continuous supportive therapy (renin-angiotensin system blockers; RASBs) when proteinuria lowers less than 1g/day, and eGFR remains stable. When proteinuria is > 1 g/day and eGFR (normal at baseline) declines to > 50 ml/min/ 1.73 m², after three months of continuous supportive therapy, patients may benefit from corticosteroids combined with supportive therapy for six months. When eGFR is less than 30 ml/min or between 30 and 50 ml/min/ 1.73 m², only supportive treatment is recommended with no immunosuppression, except for patients with rapidly progressive glomerulonephritis.

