6. SAMPLE SIZE AND STATISTICAL METHODS

ACIGAN. Data from the literature (22,23) have shown a difference in renal survival between corticosteroids and controls when the researchers assumed a difference of 50% in the primary end point (i.e. in the between-arms difference of delta 24 hour proteinuria from baseline to 6 months) as clinically relevant. Therefore, we assume that a mean delta proteinuria from baseline to 6 months in patients treated with RASBs alone (control arm) is 0.6 ± 1.0 g/24 hours (\pm SD) versus a mean delta proteinuria that is 1.2 ± 1.0 g/24 hours (\pm SD) from baseline to 6 months in patients treated with RASBs and corticosteroids (experimental arm). Based on these assumptions, we calculated a sample size of

132 patients (66 patients per group including a 10% dropout rate) for a power of 90%, a two-sided significance level of 0.05 and 3 years of recruitment. If the number of the enrolled patients will be insufficient, the recruitment period will be extended for two years.

CHRONiGaN. Data from the literature (29-31) have shown a difference of renal survival between SGLT2is and controls. There are no data in the literature exploring the difference of renal survival or proteinuria between SGLT2is and steroids. Here, the researchers assumed an opportunistic sample of 300 patients for this first comparative study (150 patients per group, including a 10% dropout rate).

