-Serum creatinine. Creatinine will be measured using enzymatic methods calibrated to the National Institute of Standards and Technology Liquid Chromatography Isotope Dilution Mass spectrometry method. Estimated (e) GFR creatinine will be estimated by the CKD-EPI formula (50). Moreover, we will calculate the slope of acute, chronic and total eGFR (51). Patients, categorized in CKD stage 1 to 3, will be included in the clinical study.

-Proteinuria. Patients will collect 24 hour urine for proteinuria and creatininuria. Values of >0.5 g/day will be considered abnormal. We will measure the time-average proteinuria (TA-P) (52) and the slope of proteinuria (53).

Serum creatinine, proteinuria, age and hypertension have a lower weight when histological lesions are not considered. This finding highlights the importance of the kidney biopsy, not only for diagnosis but for personalized treatment.

-Blood hypertension is defined when values are > 130/80 mmHg or in subjects treated with anti-hypertensive drugs. Treatment will also be conducted in hypertensive patients with blood pressure >130/80 and daily proteinuria more than 0.5 g. Sodium restriction is necessary.

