6.4 Statistical Methods

Quantitative variables will be summarized in the presence of normal distribution values as mean \pm SD or median, and interquartile ranges in the presence of non-normally distributed variables. The between-arms comparisons of continuous variables will be performed by independent t-test or Mann-Whitney U test, as appropriate. The between-arms difference of the primary end point (i.e. in the between-arms difference of delta 24h proteinuria from baseline to 6 months in the ACiGAN trial and the between-arms difference of delta 24h proteinuria from baseline to 12 months in the CHRONiGAN trial will be expressed as mean difference and 95% CI. Categorical variables will be presented as absolute and percentage frequency. Proportions will be compared using the Pearson's X^2 test or Fisher's test, as appropriate. The time to event analysis will be performed by the Kaplan-Meier curves by comparing the experimental and control group by the log rank test. Multivariate analysis will be based on Cox's regression proportional hazard method and used to assess the relative risk associated with possible baseline prognostic factors such as sex, age, serum creatinine, eGFR, hypertension, histological lesions and therapy.

The primary analysis will be conducted according to the intention-to-treat approach in all randomized patients, irrespective of adherence to the assigned treatment. A per protocol analysis will be also performed. A secondary analysis by linear mixed models (LMM) or generalized estimating equations (GEE) of repeated measurements of eGFR and proteinuria will be also performed. The choice between the two analyses will closely depend on the distribution type of the outcome variables in our study cohorts.

In these models, data will be expressed as regression coefficients, 95% CIs and P value. All analyses will be performed using SPSS for Windows, 17.0 (SPSS Inc., North Sydney, Australia) and STATA/IC 13.1 for Windows (College Station, Texas, US). A *P* value less than 0.05 will be considered statistically significant.

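### The secondary Cox model lists serum creatinine beside eGFR, age and sex, although eGFR is computed from those three, so the relative risks reported for these factors would be poorly determined

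*Protocol*

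**What the plan says.** Section 6.4 compares the arms on time to event with Kaplan-Meier curves, "comparing the experimental and control group by the log rank test". It then adds a prognostic model: "Multivariate analysis will be based on Cox's regression proportional hazard method", to be "used to assess the relative risk associated with possible baseline prognostic factors such as sex, age, serum creatinine, eGFR, hypertension, histological lesions and therapy".

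Section 6.1 fixes how the kidney function variable is obtained: "Estimated (e) GFR creatinine will be estimated by the CKD-EPI formula".

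Section 4.4.1 bases the prediction of ESKD on the MEST-C histology, eGFR, proteinuria and hypertension. It uses eGFR without creatinine, and it includes proteinuria.

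The primary endpoint in both trials is the reduction in 24-hour proteinuria (Section 4.4). The kidney composite (GFR decline above 40%, ESKD or renal death) is secondary. Section 6 sizes ACiGaN on proteinuria: "132 patients (66 patients per group including a 10% dropout rate) for a power of 90"%. Neither trial has a stated event rate or expected number of events. The only related figure is in Section 1.1: "Approximately 40% of IgAN patients reach end-stage kidney disease (ESKD) 20 years after their kidney biopsy".

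**The concern.** CKD-EPI eGFR is determined once creatinine, age and sex are known. If all four enter one Cox model, eGFR and creatinine are separated only by the curvature of the formula. The eGFR coefficient then describes the effect of eGFR with creatinine, age and sex held fixed, a contrast that no patient can show. The age and sex coefficients also change meaning, because they too are conditional on both kidney variables.

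This model exists to report a relative risk for each named factor. With the list as written, the two kidney-function relative risks would have wide intervals, could change size or sign between the two trials for no clinical reason, and could not be interpreted. That could mislead readers about prognosis, although it would not mislead them about treatment.

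**Working it through.** **1. The plan's own figure.** The protocol gives no figure for the time-to-event analyses. Its ACiGaN sample size does reproduce. With a difference of 0.6 g/24 h, SD 1.0, two-sided 0.05 and 90% power, n per arm = 2 × (1.960 + 1.282)² × 1.0² / 0.6² = 58.4, so 59. Dividing by 0.90 for dropout gives 65.6, so 66 per arm and 132 in total. That number was chosen for proteinuria, not for kidney events.

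**2. Redundancy.** The protocol does not print the CKD-EPI equation. That it takes creatinine, age and sex is a property of the formula it names. How strongly the variables overlap depends on the covariate distribution, which the protocol does not give, so the following are assumptions: age mean 42 (SD 13), 35% women, log-normal creatinine with median 1.3 mg/dL, and the entry limit of eGFR at least 30.

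- Variance inflation factor: VIF = 1 / (1 − R²), where R² comes from regressing one covariate on the others.
- R² of eGFR on creatinine, age and sex is 0.92, so VIF = 1 / 0.08 = 12.5 (12.9 with unrounded R²).
- A second set of assumed distributions gave creatinine 12.9, eGFR 12.2, sex 2.3, age 1.9, hypertension 1.0 and therapy 1.0.
- Across the checks the range for creatinine and eGFR is about 12 to 15. With creatinine removed, eGFR falls to about 1.1.

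The standard error scales with √VIF. Removing creatinine therefore shrinks the standard error of the eGFR coefficient by √(12 / 1.1) = 3.3 to √(15 / 1.1) = 3.7. Age and sex are inflated much less (√1.9 = 1.4 and √2.3 = 1.5). For them the loss is mainly one of meaning.

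**3. Effect on the therapy hazard ratio.** Simulated ACiGaN trials were run with 132 patients, 600 runs per setting, no treatment effect, and a hazard depending on eGFR, hypertension and two lesion scores. The table gives the SD of the estimated log hazard ratio for therapy.

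| Events | Therapy alone | Without creatinine (6 terms) | With creatinine (7 terms) | Increase from creatinine |
|---|---|---|---|---|
| 9 | 0.763 | 0.823 | 0.841 | 2.2% |
| 16 | 0.517 | 0.548 | 0.555 | 1.3% |
| 25 | 0.406 | 0.423 | 0.426 | 0.7% |

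The rejection rate at the null with 7 terms was 3.4%, 5.0% and 4.7%. The redundancy does not reach the treatment estimate to any useful degree. The number of events governs its precision.

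**4. Events.** The background figure is converted to three years under a constant hazard, which is an assumption:

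- hazard = −ln(1 − 0.40) / 20 = 0.0255 per year
- 3-year risk = 1 − exp(−3 × 0.0255) = 7.4%
- ACiGaN: 0.0738 × 132 = 9.7, or 0.0738 × 118 = 8.7 in completers (2 × 59)
- CHRONiGaN: 0.0738 × 300 = 22.1

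These are ESKD events only. The composite also counts a GFR decline above 40%, and the protocol gives no rate for it. For scale, assumed 3-year risks of 15%, 20% and 30% would give 19.8, 26.4 and 39.6 events in 132 patients.

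**5. What few events do to the lesion terms.** The coding of histology is not stated. If it entered as five lesion terms, the model would have 11 parameters: 9 / 11 = 0.8 events per parameter at the low end. In the simulations with 9 events, 7.7% of such fits failed or diverged when the true hazard ratio was 1, and 14.5% when it was 0.5. With 25 events none failed. These figures rest on a coding and an event count that the protocol does not state. They support caution about joint lesion effects in ACiGaN and no more.

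**The case against.** The strongest reply is that this is an open list of possible factors for a secondary model. The final covariate set and the lesion coding may be settled in an analysis plan that is not shown, and the arms are compared by the log-rank test. That stands, and it is why the point is minor. It does not remove the point, because the protocol itself names creatinine beside eGFR, age and sex.

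Section 4.6 also plans cystatin C, which would allow a combined creatinine/cystatin C eGFR. If that version were used in the model, the redundancy would be less exact. Section 6.4 does not say so, and Section 6.1 defines the creatinine-based version.

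A reader might infer several stronger things that the document does not support:

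- *That the adjusted treatment hazard ratio is overfitted because of the redundancy.* Therapy is randomised, its VIF is 1.0, and creatinine moves its SD by about 1 to 2%.
- *That ACiGaN projects a small number of events.* The protocol projects none. Nine to ten is an extrapolation of a background figure for ESKD alone, and the composite rate is unknown.
- *That an 11-parameter model is planned.* Section 6.4 fixes neither the lesion coding nor the joint entry of every factor.
- *That leaving out proteinuria is an error.* An open list does not exclude it. Naming it is an improvement.
- *That ACiGaN needs a much smaller model, with lesions estimated one at a time.* Dropping age and sex would remove the factors by which randomisation is stratified (Section 6.2). Because entry requires E1 and/or C1 (Section 4.2.1.1), every patient without E1 has crescents, so an E effect estimated without C would be confounded by eligibility.

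**Conclusion.** The concern holds in limited form. Serum creatinine is redundant in a covariate list that already contains eGFR, age and sex. Under the assumed distributions this gives VIFs of about 12 to 15 for creatinine and eGFR, and a standard error for eGFR a little over 3 times what it would be without creatinine. The relative risks reported for these factors would be imprecise and hard to interpret. The randomised therapy hazard ratio, the log-rank test and the primary proteinuria analysis are not materially affected. The exact VIFs depend on the assumed distributions of age, sex and creatinine; the redundancy follows from the named formula. Severity: minor, a free improvement.

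**What to change.** In Section 6.4, delete serum creatinine from the Cox covariates and keep eGFR with age and sex. Name baseline 24-hour proteinuria, in line with Section 4.4.1. The named items would then be therapy, age, sex, baseline eGFR, baseline 24-hour proteinuria, hypertension and histological lesions: seven, as now.

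Add a clause that joint lesion effects in ACiGaN are exploratory, and report the number of events beside the model.

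The cost is one or two sentences. No new data are needed, because proteinuria is an entry criterion measured in every patient. Nothing is lost by omitting creatinine, because eGFR carries its information.

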4.2.1 Inclusion criteria

4.2.1.1 ACIgAN study

1. Males and females aged 18 to 75 years.
2. Written informed consent form.
3. Biopsy-proven idiopathic IgAN with active renal lesions (E1 and/or C1) within 2 weeks.
4. eGFR ≥ 30 ml/min/1.73 m².
5. 24-hour proteinuria ≥ 0.5 g.
6. Patients on treatment or candidate for the treatment with RASBs (either an ACEi or ARB), as per clinical practice, according to the current KDIGO guidelines

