4.3.2 Lifestyle modifications and other therapy

Concomitant therapy

Eradication of infectious foci, or concurrent antibiotic therapy to prevent infections or to avoid the transformation of a trivial infection into a severe complication will be considered. In presence of reduced kidney function ($eGFR < 30 \text{ ml/min/1.73 m}^2$) patients will receive reduced doses of nephrotoxic antibiotics.

Non-steroidal anti-inflammatory drugs and other nephrotoxic drugs will be avoided.

Due to the short term of corticosteroid therapy, IgAN patients will not receive supplementary therapy for osteoporosis. However, the physician will decide, in every patient, the supplementary therapy.

Inactivated pneumococcal and influence vaccines will be administered. Cotrimoxazole will be administered as *Pneumocystis jirovecii* prophylaxis.

COVID-19 Vaccine will be administered also in IgAN patients who will be enrolled in the arm of corticosteroids.

Patients treated with corticosteroids will receive ciprofloxacin before and during the two weeks following the meningococcal vaccination.

In presence of hypertension, anti-hypertensive drugs will be mainly replaced by RASBs to reduce hypertension and proteinuria.

Diuretics will be administered. Thiazides will be replaced by loop diuretics in presence of impairment of the renal function less than $30 \text{ ml/min/1.73 m}^2$.

Cardioprotective drugs will be administered in presence of cardiac insufficiency.

Statins will be prescribed in presence of hypercholesterolemia (> 200 mg/dL). Allopurinol will be administered in presence of hyperuricemia. It will be reduced if patients will have an impairment of the renal function less than 30 ml/min/1.73 m².

Cimetidine will not be prescribed because it interferes with serum creatinine measurements. Other gastroprotective drugs will be administered.

In presence of persistent or permanent eGFR <15 ml/min/1.73 m² patients will receive periodic hemodialysis or peritoneal dialysis.

Any other immunosuppressive therapies e.g. mycophenolate mofetil, cyclophosphamide or azathioprine will be not permitted in this study, unless there will be other definite indications for using these drugs.

Rifampin will be also prohibited from this study as it interacts with methylprednisolone and makes the study drug less effective.

Life style modifications

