4.4 Outcome measures

The primary endpoint is the 24 h-proteinuria reduction between arms as suggested by Inker LA et al (44). It will be assessed after 4 and 8 months in the ACiGaN study and after 10 months in the CHRONiGaN trial.

The secondary end point is the GFR slope calculated as the mean of individual slope obtained from individual linear regression of eGFR overtime (3 years). Based on the International Consensus definition of clinical trial outcomes for kidney failure (23) we have also considered other secondary end points listed below.

Primary and secondary end points that will be evaluated in the two RCTs are listed below:

Primary endpoint:

- Between-arms difference in proteinuria reduction within 4 and 8 months in ACiGaN and within 10 months in CHRONiGaN study.

Secondary endpoints:

- eGFR slope calculated as mean of individual slope obtained from individual linear regression of eGFR overtime (3 years);
- eGFR decline > 40 % from the baseline value;
- composite end point: GFR decline > 40%, ESKD (defined as long-term GFR \leq 15 ml/min/1.73m² for more than three months or need for maintenance dialysis or kidney transplantation) or death due to kidney disease;
- absolute difference between last GFR value and baseline GFR;
- stable renal function defined as a decline in GFR \leq 5 ml/min/1.73m² at the end of three years follow-up;
- mean annual change in the slope of the reciprocal of serum creatinine concentration;
- time-averaged proteinuria (TA-P) calculated as the weighted mean of all post-randomization measurement, with weights representing the time elapsed since the previous measurement;
- proteinuria slope, calculated as a mean of individual slope, obtained from individual linear regression of daily proteinuria overtime (3 years);
- complete remission of proteinuria defined as achievement of urinary protein level \leq 0.2 g/day or a urinary protein-to-creatinine ratio \leq 0.2 g/g;
- partial remission of proteinuria defined as achievement of a urinary protein reduction \geq 50% or greater compared with baseline value.

The end points will be evaluated monthly in IgAN patients with active renal lesions in the first eight months after kidney biopsy and then every three months. In IgAN patients with chronic or moderate renal lesions the end points will be evaluated every three months in the first two years after the enrollment and then every six months.

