4.7 End of Study and Patient withdraw

The end of the study is defined as the last visit of the last enrolled subject.

A visit of end of study will be performed 30 days after last treatment to collect data about any adverse events and other administered therapies.

The withdraw of enrolled patients from study treatment and/or from the whole study will be done in the following conditions:

- withdraw of the informed consent
- pregnancy
- superimposed malignant diseases
- kidney failure (end-stage kidney disease)
- dialysis
- renal transplant
- non-compliance with study procedures
- Investigator judgment, for any ethical, medical, or scientific reasons
- Death.

The patient may withdraw from the treatment/trial, at any time, without penalty or loss of benefits to which he/she is otherwise entitled.

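### Section 6.4 chooses between LMM and GEE on the outcome distribution, a criterion that ignores dropout which may follow observed eGFR

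*Protocol*

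**What the plan says.** Section 6.4 of the protocol announces the analysis as follows: "A secondary analysis by linear mixed models (LMM) or generalized estimating equations (GEE) of repeated measurements of eGFR and proteinuria will be also performed". The next sentence gives the rule for picking one of the two: "The choice between the two analyses will closely depend on the distribution type of the outcome variables in our study cohorts". No working correlation, dropout weighting or missing-data assumption accompanies it.

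Three other places bear on how complete the follow-up will be:

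- Section 4.7 introduces its list with "The withdraw of enrolled patients from study treatment and/or from the whole study will be done in the following conditions". The list includes kidney failure, dialysis, renal transplant and death.
- Section 4.3.2 links dialysis to eGFR: "In presence of persistent or permanent eGFR <15 ml/min/1.73 m² patients will receive periodic hemodialysis or peritoneal dialysis".
- Sections 4.2.1.1 and 4.2.1.2 admit patients from an eGFR of 30 upwards, and Section 4.4 measures eGFR slope over three years.

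**The concern.** The rule is stated in the protocol, so this is not a detail merely left to a statistical analysis plan. It is a rule fixed on the wrong criterion. Both methods model a mean response over time, and a skewed outcome can usually be handled within an LMM by a log transformation. With incomplete follow-up, the difference that matters is the dropout each method tolerates.

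If patients leave follow-up because eGFR has fallen to the kidney-failure level, the patients who remain are those declining more slowly. Unweighted GEE then understates the decline in each arm. Where the faster-declining arm loses more patients, it also understates the difference between arms. An LMM uses each patient's observed trajectory before exit and is protected as long as exit depends on values that were recorded.

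A second issue holds for both outcomes: the estimator is settled only after the trial's own outcome data have been looked at, with no threshold stated.

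**Working it through.** **Plan's own figure.** The protocol gives no figure for this analysis. Its only calculated figure, the ACiGaN sample size in Section 6, reproduces: 2 × (1.960 + 1.282)² × 1.0² / 0.6² = 58.4, so 59 per arm; 59 / 0.90 = 65.6, so 66 per arm and 132 in total. It is not affected.

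**Inputs from the protocol.** Visits at months 0, 1, 2, 4, 6, 8, 12 and then every 3 months to 36 (Figure 2A); entry eGFR of at least 30; a kidney-failure level of 15 (Sections 4.3.2 and 4.4).

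**Assumed inputs (not in the protocol).** Mean entry eGFR 45 to 70 before truncation at 30, SD 12 to 20; slopes per year as in the table; slope SD 4 to 6; residual SD 4.

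**Model.** Patient i at time t has eGFR = b0ᵢ + sᵢ·t + error, with b0ᵢ and sᵢ varying between patients. Follow-up ends after the first observed eGFR ≤15. Each scenario is one simulated dataset of 5,000 per arm, made large to show bias rather than noise (standard error of the slope difference 0.08 to 0.12). Each method was fitted to the complete data and again to the same data after withdrawal, so sampling error largely cancels.

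Attenuation = 1 − (estimate after withdrawal / complete-data estimate).

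| Mean entry eGFR; slopes control/experimental | Withdrawn control/experimental | Complete data | GEE independence | GEE exchangeable | LMM |
|---|---|---|---|---|---|
| 70; −4/−2 | 1.9%/1.0% | 2.06 | 1.97 | 2.04 | 2.06 |
| 55; −6/−3 | 11.8%/5.9% | 2.84 | 2.33 | 2.68 | 2.84 |
| 45; −8/−4 | 32.7%/16.4% | 3.71 | 2.32 | 3.05 | 3.71 |

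Entries in the last four columns are between-arm slope differences in ml/min/1.73 m² per year. All three methods gave the same complete-data estimate.

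- Independence: 1 − 1.97/2.06 = 4%; 1 − 2.33/2.84 = 18%; 1 − 2.32/3.71 = 37%.
- Exchangeable: 1 − 2.04/2.06 = 1%; 1 − 2.68/2.84 = 6%; 1 − 3.05/3.71 = 18%.
- LMM: 0% in all three.

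**No true difference** (mean entry 45, slope −5 in both arms, withdrawal 18.5%/19.4%). The between-arm estimate was −0.16 on complete data and −0.15, −0.14 and −0.17 after withdrawal (independence, exchangeable, LMM), so the contrast is not biased. The control-arm slope did move, from −4.86 to −3.00 (independence) or −3.91 (exchangeable); LMM gave −4.84.

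**The case against.** Several stronger readings are tempting, and the documents do not support them.

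- *Unblinded data choose the model.* A reader might infer this from the open-label design. Section 6.4 speaks only of the outcome distribution in the cohorts and does not say it is inspected by arm. A pooled check need not reveal the treatment effect.
- *Skewed proteinuria is sent to GEE and so is biased.* The rule gives no direction and does not exclude transformation. The calculations above concern eGFR only. Withdrawal for kidney failure is tied directly to eGFR and only indirectly to proteinuria, and few patients entering at 30 or more should reach kidney failure within the 4 to 10 months of the proteinuria endpoints.
- *Section 4.7 makes dropout outcome-dependent as a settled fact.* Its wording covers treatment and/or the whole study. A patient who stops treatment may stay in follow-up, and Section 6.4 says "The primary analysis will be conducted according to the intention-to-treat approach in all randomized patients, irrespective of adherence to the assigned treatment". The bias arises only if eGFR collection stops as well, which the protocol does not settle.
- *The main results are at risk.* The primary comparison is a t-test or Mann-Whitney test on change in proteinuria. The eGFR-slope endpoint in Section 4.4 is defined through individual regressions, so neither LMM nor GEE produces it.

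The size can also be contested. Exit at the first observed eGFR ≤15 is stricter than the persistent level in Section 4.3.2 or the three-month ESKD definition in Section 4.4, so simulated withdrawal may be too high. The fitted LMM also has the form that generated the data, which favours it. Weighted GEE would be a valid alternative, and LMM fails if dropout depends on unobserved values.

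These points limit the reach and size of the concern. None of them supports choosing the method by distribution.

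**Conclusion.** The concern holds as a correctable fault in a secondary analysis. The selection rule rests on a criterion unrelated to validity under dropout, while the protocol allows exit that can follow observed eGFR.

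If follow-up does end at kidney failure, unweighted GEE attenuates a true eGFR slope difference by about 1% to 18% with exchangeable correlation and 4% to 37% with independence, against about 0% for LMM. These ranges rest on assumed entry eGFR, slopes and variances. The loss is negligible at 1–2% withdrawal and becomes material at roughly 6–12% and above. With no true difference and similar withdrawal in both arms, the comparison stays unbiased, although each arm's decline is understated.

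The bias concerns mainly the 3-year eGFR model. For proteinuria, the issue is chiefly that the method is chosen from the trial's data.

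**What to change.** In Section 6.4, delete the sentence that makes the choice depend on the distribution. State instead that repeated measurements will be analysed by one likelihood-based linear mixed model named in advance, with eGFR untransformed, proteinuria log-transformed, and both adjusted for baseline. Keep any GEE as a sensitivity analysis, preferably weighted for dropout and with its working correlation stated.

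The cost is one or two sentences, with no extra patients or data. There are two downsides. Proteinuria effects from this model will be reported as ratios of geometric means rather than differences in g/24 hours. The LMM still does not protect against dropout that depends on unobserved values.
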